Endpoints	
PRIMARY ENDPOINT
 
The primary safety endpoint will be the number and proportion of participants, per dose group and randomized allocation, with at least one of the following adverse events between Day 0 (Visit 2) and Day 28 (Visit 8)
 
 • Cough and spasmodic cough of grade 2 or higher. • Other respiratory tract AE related or possibly related to vaccination of grade 3 or higher. • Any other AE related or possibly related to vaccination of grade 3 or higher 
SECONDARY SAFETY ENDPOINTS
 
Number and proportion of participants, per dose group and randomized allocation, with:
 
 • at least one episode of cough or spasmodic cough, described by grade, between Day 4 and Day 28 • at least one solicited or unsolicited AEFI from respiratory tract between Day 0 and Day 28 • at least one AEFI with difficulties in breathing (asthma, spasmodic cough, pneumonia) between Day 0 and Day 28 • at least one other AEFI from the respiratory tract between Day 0 and Day 28 • at least one episode of cough, described by grade, between Day 0 and Day 28 • at least one episode of spasmodic cough, described by grade, between Day 0 and Day 28 • at least one solicited systemic AEFI between Day 0 and Day 28 (fever, headache, tiredness) • at least one unsolicited AEFI between Day 0 and Day 28 • at least one SAE related or possibly related to vaccination declared between D28 and the end of the trial 
Adverse events following immunization (AEFI) should be reported at study visits during the first 28 days of the concerned subject.
 
Serious adverse events (SAE) should be reported immediately but no later than 24 hours after detection. AEFI which lead to difficulties in breathing (asthma, spasmodic cough, pneumonia) will be considered as serious and reported to the Data Safety Monitoring Board (DSMB) and the sponsor.
 
Other secondary endpoints
 
COLONIZATION OF THE BPZE1 STRAIN IN THE NASOPHARYNGEAL MUCOSA
 
Per dose group and randomized allocation:
 
 • Number and proportion of participants who have been colonized by the modified B. pertussis strain BPZE1 at each post-vaccination visit • Number of visits during which bacteria are detected • Magnitude of bacterial colonization (number of cfu) per post-vaccination visit 
IMMUNOGENICITY
 
Per dose group and randomized allocation:
 
 • IgG and IgA antibodies against PT, FHA, PRN, and fimbriae 2/3 in serum at visits 2, 4, 6, 7, 8 and 9 
 • Geometric mean levels • Number and proportion of participants with positive responses, defined by at least 100% increase from pre- to post-vaccination, to at least 4 times MLD (minimum level of detection) after vaccination 
Sera will be tested blindly for pertussis specific IgG antibodies in batch for each group. Antibody levels to PT, FHA, PRN, and fimbriae 2/3 will be expressed in IU/mL calibrated against reference antisera from the National Institute for Biological Standards and Controls.

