XIV.3. OTHER SECONDARY ENDPOINTS

1) Colonization of the BPZE1 strain in the nasopharyngeal mucosa:

Per dose, group and randomized allocation:

- Number and proportion of participants who have been colonized by the modified B. pertussis strain BPZE1 at each post-vaccination visit
- Number of visits during which bacteria are detected
- Magnitude of bacterial colonization (number of cfu) per post-vaccination visit

2) Immunogenicity:

Per dose, group and randomized allocation:

- IgG and IgA antibodies against PT, FHA, PRN, and fimbriae 2/3 in serum at visits 2, 4, 6, 7, 8 and 9
 - Geometric mean levels
 - Number and proportion of participants with positive responses, defined by at least 100% increase from pre- to post-vaccination, to at least 4 times MLD (minimum level of detection) after vaccination

Sera will be tested blindly for pertussis specific antibodies in batch for each group. Antibody levels to PT, FHA, PRN, and fimbriae 2/3 will be expressed in IU/mL calibrated against reference antisera from the National Institute for Biological Standards and Controls.

XIV.4. EXPLORATORY ENDPOINTS

- IgG and IgA antibodies against PT, FHA, PRN, and fimbriae 2/3 in nasopharyngeal aspirate at visits 2, 4, 6, 7, 8 and 9
 - Geometric mean levels
 - Number and proportion of participants with positive responses, defined by at least 100% increase from pre- to post-vaccination, to at least 4 times MLD after vaccination
- Median levels of cytokines in nasopharyngeal aspirate
- Median levels of cytokines in cell culture supernatants after stimulation of PBMC with PT, FHA, PRN and unrelated antigen

XV. Statistical considerations

XV.1. SAMPLE SIZE CONSIDERATIONS

Acknowledging that due to the small sample size, the power of Phase I trials is in general very low, and that only frequent events can be detected with sufficient power, 12 volunteers receiving active vaccination per dose level in groups 1, 2 and 3 constitute a trade-off between detectable event rate and power in the context of a phase I trial (Buen, J Clin Pharmacol 2003). A sample size of 12 volunteers allows for observing at least one primary safety endpoint event with 80% power if the underlying event rate is at least 12.6%.

If no primary safety endpoint event is observed among 12 volunteers, the upper bound of a two-sided 95% confidence interval for the event rate would be 26%.

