1.2. TRIAL DESIGN

1.2.1. DESIGN/METHODS

This is a phase Ib, double-blinded, single center, dose-escalating study with consecutive dose groups, and a randomized placebo control group in each dose group (Groups 1 – 3). Participants will be randomized between active vaccine and placebo in a 3:1 ratio.

The volunteers will be recruited in a step-wise fashion with 16 individuals in each of three groups.

- Group 1: 12 individuals will be vaccinated once intranasally with 10^7 cfu of the organism. 4 individuals will be randomized to placebo (the diluent alone).
- Group 2: 12 individuals will be vaccinated once intranasally with 10^8 cfu of the organism. 4 individuals will be randomized to placebo (the diluent alone).
- Group 3: 12 individuals will be vaccinated once intranasally with 10^9 cfu of the organism. 4 individuals will be randomized to placebo (the diluent alone).

The administration of vaccine or diluent alone will be performed in a double-blind fashion with administration of coded vials (see below).

The volunteers in each group will be included sequentially in the study and vaccinated according to the following schedule.

The 16 individuals will be randomized as described in section VI.4 “Screening number and randomization procedure” of the protocol.

- Day 1: 2 individuals with at least 4 hours interval
- Day 2: 2 individuals with at least 4 hours interval
- Day 3: 3 individuals with at least 2 hours interval
- Day 4: 4 individuals with at least 1 hour interval
- Day 5: 5 individuals with at least 1 hour interval

Interim safety meetings with the DSMB for recommendation to the sponsor will be held before administering the next dose. At the interim safety meetings, safety data covering 28-days of post-vaccination follow-up of group 1 and group 2, respectively, will be available. Taking into account the time for the DSMB to meet and to give its recommendations for dose escalation, group 1 volunteers will have been followed up during at least 6 weeks by the time the group 2 volunteers become vaccinated. Likewise, group 2 volunteers will have been followed up during at least 6 weeks by the time the group 3 volunteers become vaccinated.

A non-controlled group (group 4) consisting of 6 individuals will be vaccinated with 10^9 cfu of the organism (open-label) to investigate the frequency of colonization in subjects with high anti-PRN antibody levels (≥ 20 IU/ml).

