2.1.3. OTHER SECONDARY ENDPOINT

1) Colonization of the BPZE1 strain in the nasopharyngeal mucosa:

Per dose, group and randomized allocation:

- Number and proportion of participants who have been colonized by the modified *B. pertussis* strain BPZE1 at each post-vaccination visit
- Number of visits during which bacteria are detected
- Magnitude of bacterial colonization (number of cfu) per post-vaccination visit
- Cough, spasmodic cough and any symptom from the respiratory tract will be described for colonized and not colonized participants

2) Immunogenicity:

Per dose, group, colonized/not colonized and randomized allocation:

- IgG and IgA antibodies against PT, FHA, PRN, and fimbriae 2/3 in serum at visits 2, 4, 6, 7, 8, 9 and 10
 - Geometric mean levels
 - Number and proportion of participants with positive responses, defined by at least 100% increase from pre- to post-vaccination, to at least 4 times MLD after vaccination

Samples will be tested blindly for *pertussis* specific antibodies in batch for each group. Antibody levels to PT, FHA, PRN, and fimbriae 2/3 will be expressed in IU/mL calibrated against reference antisera from the National Institute for Biological Standards and Controls.

- **Analysis strategy**

The immunogenicity criteria analysis will be performed on the mITT population and based on available data (without missing data handling) with the hypothesis of MCAR.

A robustness analysis will be performed and missing values will be imputed by the median of immunogenicity values in the placebo group.

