3.3.3. BIOLOGICAL CHARACTERISTICS

- Laboratory sampling (taken or not)
 - Blood sample for *pertussis* antibodies
 - Blood sample for clinical chemistry and hematology
 - Blood sample for HIV, hepatitis B and C
 - Urine safety analysis
 - Urine drug screen
 - Reason for not have been taken the sample
- Laboratory results
 - Screening of HIV (positive/negative)
 - Screening for hepatitis B (positive/negative)
 - Screening for hepatitis C (positive/negative)
 - Screening for anti-PT *pertussis* IgG antibodies in serum (in classes : < 20 IU/ml; ≥ 20 IU/ml)
 - Screening for anti-pertactin *pertussis* IgG antibodies in serum (in classes : < 20 IU/ml; ≥ 20 IU/ml)
- Urine analysis (in classes: normal/abnormal, not clinical significant/abnormal, clinical significant)

- U-Erythrocytes
- U-Leucocytes
- U-Protein
- U-Glucose
- U-Ketones
- U-Nitrites
- U-pH

- Drug screen (negative or positive)
 - Cocaine
 - Amphetamine
 - Methylene dioxymeth-amphetamine
 - Morphine
 - Benzodiazepines
 - Cannabis

- Hematology and blood chemistry (in classes: normal/abnormal, not clinical significant/abnormal, clinical significant)
 - Hemoglobin
 - RBC
 - WBC
 - Neutrophil
 - Lymphocyte
 - Monocyte
 - Eosinophil
 - Basophil
 - Platelets
 - Potassium
 - Calcium
 - Sodium
 - Creatinin
 - Albumin
 - Bilirubin
 - Alkaline phosphatase
 - Alanine amino transferase
 - Glutamytransferase
 - C-reactive protein
 - Blood glucose
 - Thyroidea stim. hormone

3.4. POOLING OF PARTICIPANTS ALLOCATED TO PLACEBO IN GROUPS 1, 2 AND 3

The description of the following characteristics will be used to assess whether participants allocated to placebo are described in groups 1, 2 and 3 can be pooled in the analysis:

- Age at screening (in years),
- Sex,
- BMI at D00 (in kg/m²),
- Occurrence of cough during follow-up in placebo recipients,
- IgG and IgA antibody titers in placebo recipients at 14 and 28 days to the following antigens:
 - PT
 - FHA
 - PRN
 - Fimbriae 2/3

Pooling of placebo recipients for all following analyses will be done if no clinically significant differences between groups (corresponding to different calendar enrolment periods) are observed.

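### Testing antibodies group by group ties assay run to dose group, so cross-group titre displays and the SAP 3.4 placebo-pooling decision can pick up assay shift

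*Combined protocol and SAP*

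**What the plan says.** Protocol XIV.3 sets the testing order: "Sera will be tested blindly for pertussis specific antibodies in batch for each group". The synopsis has the same rule worded for IgG only: "Sera will be tested blindly for pertussis specific IgG antibodies in batch for each group". SAP 2.1.3 repeats it for samples generally: "specific antibodies in batch for each group". Both documents add that levels "will be expressed in IU/mL calibrated against reference antisera from the National Institute for Biological Standards and Controls".

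SAP 1.2.1 describes a "dose-escalating study with consecutive dose groups, and a randomized placebo control group in each dose group (Groups 1 – 3"), each with 12 active and 4 placebo participants. Group 4 is six open-label participants who receive the Group 3 dose, with no placebo.

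SAP 3.4 decides whether the three placebo sets may be combined. Beside age, sex, BMI and cough it lists "IgG and IgA antibody titers in placebo recipients at 14 and 28 days to the following antigens" (PT, FHA, PRN and fimbriae 2/3). The rule is: "Pooling of placebo recipients for all following analyses will be done if no clinically significant differences between groups". It equates group with calendar enrolment period, does not mention assay run, and gives no numerical threshold.

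No between-group tests are planned (protocol XV.2.1, SAP 2.2.2). GMTs with 95% intervals are displayed per group, and protocol XV.2.3 describes titres for each vaccine group and for pooled placebo.

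**The concern.** If the sera of one group are tested together and apart from the other groups, a shift between assay runs cannot be told from a difference between dose groups. The 95% intervals printed beside the GMTs contain participant variation only, so a reader who sets the groups side by side has no signal that part of a gap may come from the laboratory.

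The second route is the pooling rule. It compares raw placebo titres between groups, and under this layout each group's titres carry that group's run shift. The SAP would read such a shift as a calendar effect. Because the rule governs every later analysis, an assay artefact could split the placebo comparator in the safety tables, where serology plays no part.

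Nothing in the documents appears to require group-wise serology. The DSMB reports (protocol XIII.7, SAP 3.10) use adverse events. The Phase II interim (SAP 2.1.6 and 3.11) uses safety, culture, haematology and baseline data. Antibody results stay inside the laboratory until the study is complete (protocol II.3), apart from access for the interim statistician, and sera are stored frozen (protocol XII.3). Eligibility testing for PT and PRN uses a separate Visit 1 sample.

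**Working it through.** **1. The plan's own figures.** The exact two-sided 95% upper bound for zero events in n is 1 − 0.025^(1/n).
- n = 12: 26.5% (plan: 26%).
- n = 36: 9.7% (plan: 10%).
- Event rate giving 80% power to see at least one event in 12: 1 − 0.2^(1/12) = 12.55% (plan: 12.6%).

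All three reproduce.

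**2. Spurious ratio of two GMTs.** The documents give no between-run CV, so 10%, 20% and 30% are assumptions, with one run per group. The run SD on the ln scale is s = √ln(1 + CV²), and the 95% factor for the ratio of two groups with no true difference is exp(1.96 × √2 × s).

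| CV | s | Factor, one run per group | Factor, three independent runs per group |
|---|---|---|---|
| 10% | 0.0998 | 1.32 | 1.17 |
| 20% | 0.1980 | 1.73 | 1.37 |
| 30% | 0.2936 | 2.26 | 1.60 |

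The last column divides s by √3.

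**3. Like-for-like sampling error.** For a ratio of two GMTs with n = 12 per group and an assumed ln-SD of 0.8, SE = 0.8 × √(2/12) = 0.3266. With t = 2.074 on 22 df, the CI factor is exp(2.074 × 0.3266) = 1.97. The one-run artefact is below this at 10% and 20% CV and above it only at 30%.

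**4. Effect on an interval that ignores run.** Coverage of a nominal 95% interval for that ratio is 2Φ(1.96 × SE / √(SE² + 2s²)) − 1. This gives 93%, 86% and 77% at CV 10%, 20% and 30%.

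**5. The pooling rule.** Two isotypes × four antigens × two days make 16 summaries, each on 4 participants per group. A simulation (20,000 replicates, no true group difference) assumed a day 14/day 28 correlation of 0.9 and took a 2-fold gap among the three placebo GMTs as a difference. The threshold and SDs are assumptions. Run SDs of 0.05/0.10/0.15 log10 correspond to CVs of about 12/23/36%.

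| Participant SD (log10) | One summary shows a gap: no run effect | Run SD 0.05/0.10/0.15 | Any of 16 shows a gap: no run effect |
|---|---|---|---|
| 0.2 | 8% | 13/28/46% | 63% |
| 0.3 | 33% | 37/46/57% | 99% |
| 0.4 | 54% | 56/61/67% | >99% |

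Judged on change from baseline with pre and post sera in one run, the run shift cancels. The figures are then 0-1% per summary and 0-19% for any of 16 (SD of change 0.05-0.15 log10, assumed).

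**6. If pooling is lost.** The upper bound for zero placebo events is 1 − 0.025^(1/4) = 60.2% in each group of 4, against 26.5% for 12 pooled.

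**The case against.** The case against has real force. Calibration to reference antisera stands beside the batching rule, and its purpose is to reduce run shift; the residual CV may be small. Sixteen participants with six serum visits make 96 sera for eight antigen-isotype assays, which could take several runs per group and would shrink the factors as in step 2. Run layout and controls may be set out in the Laboratory analytical plan, which is not available. All of this stands, and it limits how large the problem can be said to be.

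The main contrasts are also protected. Each group's batch contains its own 4 randomized placebo recipients, and the planned tests are paired changes within group. If pre and post sera share a run, the shift cancels in those tests and in the 100% increase criterion, though not in the responder floor of four times the minimum level of detection. A reader might infer that the vaccine's antibody effect is itself confounded; the documents do not support that.

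A reader might also infer that Phase II dose selection would rest on distorted titres. The planned Phase II interim contains no serology, so that link is not supported.

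Finally, the pooling rule is fragile even with no run effect (step 5), so common runs alone would not repair it. That is correct, and is why SAP 3.4 must change as well. What the objection does not remove is the aliasing: no between-group test is planned, but the titres are still displayed side by side and still enter the pooling decision.

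**Conclusion.** The point holds in a limited form. Assay run coincides with dose group and calendar period for Groups 1-3 and with group for Group 4, and the available documents contain no means of separating them beyond calibration. The exposed outputs are GMTs read across groups, active against pooled placebo, Group 4 against Group 3 (which has no within-batch placebo anchor in Group 4), and the SAP 3.4 pooling decision.

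Under the assumed CVs and one run per group, the artefact factor is 1.32 to 2.26 against a sampling factor of 1.97. A reader might infer that run shift matches or exceeds sampling error in general. On these assumptions it does so only at 30% CV, and less with several runs per group.

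Nor does the primary safety endpoint become biased in the active arms: those estimates are unchanged. The effect on safety is confined to the placebo display. It arises only if a shift survives calibration and is then judged clinically significant, in which case the zero-event bound is 60.2% instead of 26.5%.

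**What to change.** **Assay layout (protocol XIV.3, synopsis, SAP 2.1.3, Laboratory analytical plan).** Replace group-wise batching with runs balanced over groups and over vaccine and placebo under blinded codes, with each participant's sera through Visit 9 in the same run. Include a fixed set of bridging sera in every run, including the later runs for Visit 10, and adjust for or report run differences. Visit 10 sera cannot join the main runs without delaying the separate 6-month report (SAP 1.4), hence the bridging. If group-wise testing is kept for timing, use the bridging sera alone.

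**Pooling rule (SAP 3.4).** Judge pooling for immunogenicity on change from baseline, with a stated threshold. Remove antibody titres from the pooling decision for safety endpoints.

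**Cost.** A few extra assay wells and wording changes. With balanced runs, serology for the earlier groups waits for the last group's Visit 9 sera. Group 4 vaccination began in March 2016 (SAP 1.2.2), so that is about September 2016, just before the planned October 2016 analysis start. The one-month visit window could use up that margin. The SAP's assay calendar runs to April 2017, and the bridging-only option avoids the wait.

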Appendix 2. Environment risk assessment for *B. pertussis* strain BPZE1

[figure not shown]
[figure not shown]
[figure not shown]

1. TRIAL SUMMARY

1.1. TRIAL OBJECTIVES

1.1.1. MAIN OBJECTIVE

To assess the general safety and tolerability in the respiratory tract including specific adverse events such as cough/spasmodic cough, during the 4- 28 days after vaccination by a single ascending dose of the genetically modified *B. pertussis* strain BPZE1 in healthy adult volunteers.

1.1.2. SECONDARY OBJECTIVES

To assess after vaccination by a single ascending dose of the genetically modified *B. pertussis* strain in healthy adult volunteers:

1. the safety and tolerability of the vaccine over 6 months (group 1-4) and then 12 months (group 1-3) post-vaccination
2. the frequency of colonization of the human respiratory tract by live attenuated *B. pertussis* strain and its magnitude (in terms of colony forming units) over 28-days post-vaccination.
3. the levels of serum IgG and IgA antibodies to 4 different *B. pertussis* antigens (*pertussis* toxin (PT), filamentous hemagglutinin (FHA), pertactin (PRN), and fimbriae 2/3) over 6 months (group 1-4) and then 12 months (group 1-3) after vaccination.

Exploratory objectives

To assess the B and T cell immune responses to 4 different *B. pertussis* antigens (*pertussis* toxin (PT), filamentous hemagglutinin (FHA), pertactin (PRN), and fimbriae 2/3) over -12 months after vaccination by :

- the levels of IgA in nasopharyngeal aspirate.
- the cytokine levels in nasopharyngeal aspirate.
- the levels of secreted cytokines as well as the number of pertussis-specific T- and memory B-cells after stimulation of PBMC with *B. pertussis* antigens and unrelated antigens.
-

To explore the frequency and magnitude of colonization and as well as antibody, B and T cell responses in a small group of healthy adult volunteers with high PRN antibody levels (only highest vaccine dose).

1.2. TRIAL DESIGN

1.2.1. DESIGN/METHODS

This is a phase Ib, double-blinded, single center, dose-escalating study with consecutive dose groups, and a randomized placebo control group in each dose group (Groups 1 – 3). Participants will be randomized between active vaccine and placebo in a 3:1 ratio.

The volunteers will be recruited in a step-wise fashion with 16 individuals in each of three groups.

- Group 1: 12 individuals will be vaccinated once intranasally with 10^7 cfu of the organism. 4 individuals will be randomized to placebo (the diluent alone).
- Group 2: 12 individuals will be vaccinated once intranasally with 10^8 cfu of the organism. 4 individuals will be randomized to placebo (the diluent alone).
- Group 3: 12 individuals will be vaccinated once intranasally with 10^9 cfu of the organism. 4 individuals will be randomized to placebo (the diluent alone).

The administration of vaccine or diluent alone will be performed in a double-blind fashion with administration of coded vials (see below).

The volunteers in each group will be included sequentially in the study and vaccinated according to the following schedule.

The 16 individuals will be randomized as described in section VI.4 “Screening number and randomization procedure” of the protocol.

- Day 1: 2 individuals with at least 4 hours interval
- Day 2: 2 individuals with at least 4 hours interval
- Day 3: 3 individuals with at least 2 hours interval
- Day 4: 4 individuals with at least 1 hour interval
- Day 5: 5 individuals with at least 1 hour interval

Interim safety meetings with the DSMB for recommendation to the sponsor will be held before administering the next dose. At the interim safety meetings, safety data covering 28-days of post-vaccination follow-up of group 1 and group 2, respectively, will be available. Taking into account the time for the DSMB to meet and to give its recommendations for dose escalation, group 1 volunteers will have been followed up during at least 6 weeks by the time the group 2 volunteers become vaccinated. Likewise, group 2 volunteers will have been followed up during at least 6 weeks by the time the group 3 volunteers become vaccinated.

A non-controlled group (group 4) consisting of 6 individuals will be vaccinated with 10^9 cfu of the organism (open-label) to investigate the frequency of colonization in subjects with high anti-PRN antibody levels (≥ 20 IU/ml).

